Oficial title

Polypectomy With Hot vs Cold Snare in Small Colonic Lesions

• Valladolid (Spain), 17 November 2018

Abstract

Colonoscopy is the technique of choice for the diagnosis and prevention of colorectal cancer (CRC). The identification and extirpation of adenomas decreases the incidence of CRC by up to 76%. More than 70% of the excised lesions are less than 10 mm. There is controversy about the technique to be used (resection with cold vs hot snare) in the lesions of 5-9mm. Both use a polypectomy snare, differing in that the cold handle cuts by friction, while the hot snare uses electrical current. We propose a multicentre randomized clinical trial comparing both endoscopic techniques. At least 394 injuries per group will be included, randomizing patients to whom a diagnostic colonoscopy is requested for symptoms, screening or revision protocols. Randomization will be performed stratified by endoscopist. The primary objective is the proportion of incomplete polypectomies, which will be analyzed centrally from random biopsies of the edges of the lesion. As secondary objectives, we will compare the proportion of immediate and delayed hemorrhagic complications, the evolution of postprocedural abdominal pain and the factors associated with incomplete excision in each group and the factors associated with a failed cold polypectomy. The analysis of the primary objective will be carried out by means of the z test of homogeneity without using the correction of Yates, estimating the confidence interval of the difference between both groups. The analysis will be carried out by intention to treat and by protocol.

1. Introduction

Colorectal cancer (CRC) is a major cause of morbidity and mortality worldwide. It is estimated that in 2008, 1233,000 new cases were diagnosed and more than 600,000 people died for this reason throughout the world (1). Colonoscopy is the technique of choice for both diagnosis and prevention (2), since the identification and removal of colonic adenomas reduces the incidence of CRC by up to 76% (3-7).

Different endoscopic techniques have been developed for the removal of adenomas; The choice of some over others is made according to the size, morphology and location of the lesion.

In lesions of 5-9 mm there is controversy about the relevance of using the hot or cold handle. Both techniques use the same instrument, a polypectomy loop, differing in the cut they make. In the cold snare the cut is produced by the friction of the metal snare on the mucosa, while in the hot snare, the passage of electrical current through the snare generates an increase in temperature that makes the cut. These differences condition that, although they use the same instrument, both techniques present significant differences in their execution.

The studies focused to compare endoscopic resection techniques focus on 3 main objectives: effectiveness (ability to completely remove the lesion), safety (presence of complications during the procedure or during follow-up) and associated symptomatology (duration and intensity of abdominal symptoms). after the colonoscopy). Currently there is few data available to evaluate the ideal technique in polyps of this size.

Regarding complications, in 2011 Paspatis et al published an essay comparing the cold snare (208 patients) with the hot snare (206) for the exeresis of polyps between 3 and 8 mm (8).

They focused on the immediate hemorrhagic complications, which were more frequent in the cold-snare group, but resolved spontaneously in all cases. The only study available that compares both techniques in polyps of 5-9 mm is a retrospective single-center study. a total of 148 injuries analyzed (9). They did not observe differences between the deferred complications between both groups (1.3% and 1.4%). Ichise et al published a randomized clinical trial evaluating abdominal symptoms after polypectomy, including 40 patients per group. The presence of abdominal symptoms (abdominal pain, diarrhea) in the two weeks following the examination was more frequent in the hot snare group (20% vs 2.5%) (10).

The evaluation of the resections can be done by several methods, which conditions the disparity observed in the different works. The ideal method would be the evaluation of the margins of lateral and vertical resection. However, this is complicated by the usual handling of the samples (fragmented samples, samples submitted for histological study in pot instead of mounted ...), so the number of non-valuable samples can reach 40% (11). Another option is to take biopsies from the edges of the lesion. Although it includes a component of subjectivity, depending on where the biopsies are taken, it allows to evaluate all the injuries. In 2010, Pohl et al published a paper based on data from 2 North American centers (12). All resections were made with hot loop, being incomplete in 6.8% of the lesions <10 mm. The cold loop technique presents similar results. In a study in which 59 slightly smaller polyps were analyzed (average size 3.7 mm), incomplete resections were observed in 6.8% (13). The studies in which the edges of resection are evaluated show greater proportions in both techniques. The work published in 2015 by Din and colleagues, comparing two techniques of cold cutting in lesions of 3-7 mm, observed a proportion of incomplete polypectomies close to 30% (14) while another retrospective observational work with 175 lesions of 3-10 mm extirpated with cold snare and 1010 of 6-15 mm excised with hot snare, the proportion of histologically complete polypectomies was 53% and 61%, respectively (15).

2. Hypothesis

Conceptual hypothesis:

Cold snare polypectomy presents a proportion of incomplete polypectomies similar to polypectomy with hot snare.

Operational hypothesis:

Two endoscopic techniques will be compared from two groups created by a random assignment to one or another type of polypectomy, evaluating the proportion of non-excised polypoid tissue after it. This will be done from random biopsies of the edges of the lesion and possible macroscopic remnants

3. Objectives.

Primary objective:

To compare the proportion of incomplete polypectomies in both types of polypectomy (cold snare vs. hot snare).

Secondary objectives:

- ²Compare the proportion of immediate and delayed bleeding complications, total and according to the severity that they present according to the ASGE classification.
- ² Compare the evolution of abdominal pain in the 5 hours postprocedure between both groups.
- $^{\fbox{2}}$ Evaluate the factors associated with an incomplete extirpation in each group.
- ² Evaluate the factors associated with a failed cold polypectomy.

4. Design

Randomized clinical trial comparing two endoscopic techniques.

5. Methods

Population to study

The study population includes patients scheduled to perform a colonoscopy in a non-urgent way. The patient will be invited to participate before performing the colonoscopy.

The variables defined in Annex 1 will be collected in a dissociated form database.

Inclusion and exclusion criteria

The inclusion criteria are:

• Patients older than 18 years scheduled to undergo a colonoscopy.

The exclusion criteria are:

- Absence of lesions of 5-9 mm.
- Contraindication for polypectomy (anticoagulant treatment, treatment with clopidogrel, coagulopathy or severe thrombocytopenia)
- Loss of polypectomy specimen
- Refusal to participate

Randomization

It will be done once the patient agrees to participate in the work and the first candidate polyp has been identified. Each patient will be randomized (regardless of the number of injuries per patient) in such a way that all lesions of each patient will be removed in the same way. It will be stratified by endoscopist, in such a way that each endoscopist will have its sequence of sealed randomization. Within each stratum a pure randomization will be carried out through a sequence generated by computer where the probability of belonging to each group will be 0.5. A total of 60 numbered sealed opaque envelopes will be available for each endoscopist that will be stored in the endoscopy room and will be opened consecutively as patients are included.

Intervention

Patients who meet the inclusion criteria and do not present any exclusion criteria (preendoscopic) will be invited to participate in the study. The informed consent will be completed according to the law 41/2002 of autonomy of the patient without it being altered the relationship with your doctor or any damage to your treatment.

1) Endoscopic act

The interventions will be carried out in each of the participating centers. The scans will be performed under sedation according to the protocols established in each center. Once the lesion is identified, the method of extirpation of the lesion will be randomized.

- Cold Group: polypectomy with a cold snare will be carried out according to the usual standards recommended by international societies. As far as possible we will try to arrange the lesion in the position equivalent to 5 o'clock on the dial, the end of the snare will be placed several millimeters from the lesion and the tip of the catheter will be angled downwards as the Asa, without aspiration at any time to avoid entrapment of the submucosa.
- -Hot Group: polypectomy with snare connected to the electrosurgical unit according to the standards recommended by international societies, using a mixed current (cut-coagulation). Once the lesion is captured, the snare is pulled to slightly separate it from the surrounding mucosa before polypectomy. Elevation of the lesion prior to polypectomy will not be performed.
- -Common evaluation: once the polypectomies are completed, the basis of the polypectomies will be evaluated, taking biopsies from any suggestive area and also 2 random biopsies at the base of the polypectomy.

2) Postendoscopic follow-up

After a minimum of 21 days and a maximum of 28 days from the endoscopic examination, the patient will be contacted by telephone to collect the form about the evolution of the abdominal symptoms and to collect data about the appearance of complications (questions will be asked about visits to the hospital and in a targeted manner about the most frequent symptoms of the usual complications (fever, hemorrhage, abdominal pain).

3) Histological analysis

The analysis of the specimens of the polypectomies will be carried out in each center according to their usual protocol. The analysis of the biopsies of the base of the polyp will be carried out centrally by a pathologist with more than 5 years of experience in digestive pathology. Samples from the base of the polyp will be sent biweekly from each center to the university health care complex in Salamanca through a messenger service. The pathologist will be blinded regarding the histological diagnosis of the excised polyp and the type of polypectomy (although it is true that it is difficult to blind this last point since the presence of heat artifacts in those removed with a hot handle is very frequent). The samples sent for centralized analysis will not be conserved, but will be destroyed once the study is completed according to the usual protocols.

Sample size

Assuming a proportion of incomplete polypectomies in both groups of 10% (using the taking of biopsies as a diagonostic pattern) and setting an equivalence limit of 7%, a total of 315 lesions per group are estimated to have an α risk of 5% and a power of 80%. Assuming a proportion of losses (polyps not recovered for histological study, polypectomies of the failed Cold group of 20%), an estimated 394 lesions per group are needed, with a total of 788 lesions in total.

Data Collect

All the variables concerning the characteristics of the endoscopist, the patient and the injuries included will be collected in each center. The variables related to the histological diagnosis will be collected in the same way in the respective center. The variables concerning the follow-up will be collected in a centralized manner, through a telephone call that will be made between 3 and 4 weeks from the procedure. The variable related to the histological study of the base of the polyp will be collected in a centralized manner by the pathologist in charge of the analysis of the samples.

6. Data management

Data from the data collection notebooks will be merged by the main researcher or collaborating researchers anonymously, encrypted and dissociated from the clinical information by means of a patient identification code (ID), in a database made through the program Access (Microsoft Corporation, Redmond, WA USA). A copy of the database will be used in each participating center, which will be merged after completing the data collection. The responsible researcher will define an ID for each participant. The data entered in the

database will be anonymous and the database will be protected with a password to which only the researchers will have access.

The unified file will be kept at the Río Hortega University Hospital and will be maintained until the end of the study. Regarding the application of the Organic Law on Data Protection 15/1999 and Royal Decree 1720/2007 that develops it, it should be noted that the protocol defined in the project oriented to epidemiological analysis, determines that the files will record information completely anonymized

7. Statistical analysis

The Access program (Microsoft Corporation, Redmond, WA USA) will be used for the realization of the database and the statistical analysis of them will be carried out through the STATA program (StataCorp, 2013. Stata Statistical Software: Release 13. College Station, TX: StataCorp LP). In the quantitative variables, the arithmetic mean and the standard deviation will be calculated (variables that do not follow a normal distribution according to the Kolmogorov-Smirnov test will be described with median, minimum, maximum and interquartile range), and the qualitative ones will be expressed as percentages and your 95% confidence intervals.

The analysis of the primary objective, the proportion of incomplete polypectomies in both groups will be compared by means of the z test of homogeneity without using the correction of Yates. The confidence interval of the difference between the two groups will also be estimated. The analysis will be carried out by intention to treat, regardless of the type of polypectomy performed and per protocol (assigning the lesions assigned to the group Cold that are extirpated with hot snare to the Hot group). To evaluate possible confounding factors (endoscopist, nurse, handle type, location ...), the STATA confound user command will be used, defining as a significant change that which conditions a change in the odds ratio greater than 10% with respect to the one obtained with the complete model. In case several models do not present differences greater than 10%, the most parsimonious will be chosen.

Within the secondary objectives, the proportion of complications in both groups will be verified by the de2 test. To evaluate the factors associated with incomplete polypectomies and those associated with failed cold polypectomy, multivariate logistic regression techniques will be used.

8. Ethical aspects

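### Specimen loss is listed as an exclusion, but it can arise only after randomisation and the primary-outcome biopsies do not depend on retrieval, so dropping these lesions conflicts with the planned ITT analysis

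*Combined protocol and SAP*

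**What the plan says.** The exclusion list in section 5 includes "Loss of polypectomy specimen", next to conditions that can be checked before the procedure. The Randomization paragraph places allocation after consent and once "the first candidate polyp has been identified". Allocation is by patient, with one technique for all of that patient's lesions. The Intervention paragraph applies only the pre-endoscopic exclusions at invitation.

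For both arms, the Endoscopic act paragraph calls for "taking biopsies from any suggestive area and also 2 random biopsies at the base of the polypectomy". It attaches no condition about retrieving the polyp. Under Histological analysis, each centre reads its own polyp specimens, while the base biopsies are read centrally: "The pathologist will be blinded regarding the histological diagnosis of the excised polyp".

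The Sample size paragraph lists as losses "polyps not recovered for histological study, polypectomies of the failed Cold group of 20" per cent. Section 7 states: "The analysis will be carried out by intention to treat, regardless of the type of polypectomy performed". It also plans a per-protocol analysis, defined by "assigning the lesions assigned to the group Cold that are extirpated with hot snare to the Hot group". Neither definition says what happens to a lesion whose specimen is lost.

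**The concern.** An exclusion criterion should be settled before allocation, or at least be unaffected by it. Specimen loss is neither. It follows the resection, and the endoscopist who resects and retrieves knows the arm. Equal loss in the two arms cannot be presumed.

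If lesions leave the analysis for this reason, the groups compared are no longer those formed by randomisation. If loss differs by arm and lost lesions differ in completeness, the comparison of incomplete resection is biased. In an equivalence trial a bias in either direction can change the conclusion.

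The criterion also sits in a patient-level list, and the plan does not say whether the lesion or the whole patient is removed. The sample-size wording points to lesions. Read literally, though, a patient with one lost specimen would also leave the bleeding and pain analyses, where the specimen plays no part.

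**Working it through.** **Order of events.** From section 5: consent, first candidate polyp seen, envelope opened, resection, retrieval or loss, base biopsies, separate local and central readings. Loss lies after allocation on any reading. No visible eligibility rule depends on specimen histology: entry rests on having a 5-9 mm lesion.

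**The plan's own figures.** Inputs from the Sample size paragraph: 10% incomplete in both groups, limit 7 points, α 5%, power 80%, losses 20%. For equivalence by two one-sided 5% tests:

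n = 2 × 0.10 × 0.90 × (1.645 + 1.282)² / 0.07² = 314.6, so 315 per group.

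315 / 0.80 = 393.75, so 394 per group, an allowance of 394 - 315 = 79 lesions per group. Both figures reproduce. With power = 2Φ(0.07/SE - 1.645) - 1 and SE = √(0.18/n), power is 80.1% at 315 and 89.7% at 394, treating lesions as independent as the plan does. Power is therefore not the issue.

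**Possible bias.** Let l be the share of lesions lost in an arm and r the incomplete rate among lost lesions. With a true rate of 10%, the rate seen after dropping them is

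(0.10 - l × r) / (1 - l).

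All l and r values are assumptions, and r is taken as the same in both arms. Differences are higher-loss arm minus lower-loss arm.

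| Loss | r | Higher-loss arm | Lower-loss arm | Difference (points) |
|---|---|---|---|---|
| 5% vs 2% | 0% | 10.53% | 10.20% | +0.32 |
| 5% vs 2% | 10% | 10.00% | 10.00% | 0 |
| 5% vs 2% | 20% | 9.47% | 9.80% | -0.32 |
| 5% vs 2% | 30% | 8.95% | 9.59% | -0.64 |
| 15% vs 5% | 0% | 11.76% | 10.53% | +1.24 |
| 15% vs 5% | 10% | 10.00% | 10.00% | 0 |
| 15% vs 5% | 20% | 8.24% | 9.47% | -1.24 |
| 15% vs 5% | 30% | 6.47% | 8.95% | -2.48 |

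The true difference is 0 throughout. With common r, equal loss in both arms gives no bias, and neither does r = 10%. The 15% case is an upper end, because the 20% allowance also has to cover failed cold polypectomies.

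**Cost of keeping the lesions.** Assume that non-neoplastic lesions cannot contribute a difference between arms and are equally common in both. If 5% of lesions are retained without histology and all are non-neoplastic, a true 7-point difference reads as 7 × (1 - 0.05) = 6.65. If half are, it reads as 7 × (1 - 0.025) = 6.83.

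**Lesions with no base biopsy result.** Let a share m be missing in each arm, with 10% incomplete among observed lesions. Counting missing as incomplete in Cold and complete in Hot gives [0.10(1 - m) + m] - 0.10(1 - m) = +m. The mirror case gives -m. So m = 1% (about 4 of 394) moves the difference by 1 point, and m = 2% (about 8) by 2 points, in either direction.

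**The case against.** The best defence is that this is a deliberate evaluability rule filed under the wrong heading. The authors mark some exclusions as pre-endoscopic, allow for unrecovered polyps in the lesion count, and explain ITT only in terms of crossover between techniques. They may also want specimen histology to link residual tissue to the original lesion. Blinding the central reader to that histology does not prove that the endpoint is classified without it, and Annex 1, which defines the variables, is not in the text available.

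Part of this stands. The plan does not say that biopsies are still taken once a loss is noticed, and section 8.1 describes them as the only departure from usual practice, so an explicit instruction is needed. Retaining lesions of unknown histology can also pull the arms together, which favours equivalence. But an allowance in the sample size protects power and not comparability. Nor does the rule work as a histology filter: under the visible criteria a retrieved non-neoplastic lesion stays in.

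Two stronger readings should be resisted. A reader might take the Introduction's remark that "it allows to evaluate all the injuries" as a promise covering lost specimens. It contrasts biopsies with margin reading, where handling makes some samples unassessable, and says nothing about loss. A reader might also infer that the exclusion depends on the biopsy result, or that it cannot. The documents do not say when loss is established relative to the reading, so neither follows.

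**Conclusion.** The point holds as a conflict between a stated rule and the planned ITT analysis: randomised lesions are dropped for a post-allocation event although the plan orders the primary-outcome biopsies regardless of retrieval.

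It does not establish that the result will be biased. The documents give no loss rate by arm and no incomplete rate among lost lesions, so size and direction are unknown. Bias is zero if loss is unrelated to completeness, or if loss is equal by arm and lost lesions have the same incomplete rate in each. The illustrative shift is under 1 point at 5% vs 2% loss and at most about 2.5 points at 15% vs 5%, against a limit of 7.

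It is tempting to go further and give the whole 20% allowance to lost specimens in one arm and none to the other. With 30% incomplete among those lost, that yields (0.10 - 0.20 × 0.30)/0.80 = 5% vs 10%, a 5-point shift. The documents do not support this, because the allowance is shared with failed cold polypectomies and no split is given.

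The change is worth making because it is cheap, not because a large bias has been shown.

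**What to change.** - Delete specimen loss from the exclusion criteria, and state in the Endoscopic act paragraph that the base biopsies are taken whether or not the specimen is retrieved.
- In section 7, keep every randomised patient, and every eligible lesion with a base biopsy result, in the ITT primary analysis. Keep all randomised patients in the bleeding and pain analyses.
- Report specimen loss by arm.
- Add a sensitivity analysis that excludes the affected lesions but not the patients.
- For lesions with no base biopsy result, add worst-case analyses in both directions (missing counted as incomplete in Cold and complete in Hot, then the reverse), because the limit is an equivalence limit.
- State that for ITT the 20% allowance covers only lesions without a base biopsy result. Failed cold polypectomies remain in Cold under ITT and move to Hot under the per-protocol rule, so neither analysis loses them.

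The cost is protocol and SAP wording. The biopsies are already ordered for all resections, and 394 per group need not change on this account. The downside is the dilution from retained lesions of unknown histology; the lesion-exclusion sensitivity analysis will show whether it matters.

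### Patients are randomised but lesions are counted and tested as independent: the sample size, primary test, interval and logistic models make no allowance for within-patient correlation

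*Combined protocol and SAP*

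**What the plan says.** Section 5, Randomization, makes the patient the unit of allocation, whatever the number of lesions, so that "all lesions of each patient will be removed in the same way". No cap on lesions per patient is given.

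Section 5, Sample size, counts lesions. With 10% incomplete polypectomies in both groups and an equivalence limit of 7%, "a total of 315 lesions per group are estimated" for an α risk of 5% and 80% power. After a 20% allowance for losses, "an estimated 394 lesions per group are needed".

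Section 7 also works by lesion. The proportions of incomplete polypectomies "will be compared by means of the z test of homogeneity without using the correction of Yates", and "The confidence interval of the difference between the two groups will also be estimated". For the factors linked to incomplete excision and to failed cold polypectomy, "multivariate logistic regression techniques will be used".

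Neither section mentions a design effect, an ICC, an expected number of lesions per patient, generalised estimating equations (GEE), a random effect or a cluster-robust variance.

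**The concern.** Two lesions from one patient share the patient, the session and the endoscopist, so their outcomes may be more alike than those of lesions from different patients. Because all of a patient's lesions sit in the same arm, positive correlation can only increase the variance of the difference between arms; nothing cancels within a patient.

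A z test and interval that treat lesions as independent would then use too small a standard error. Three things follow:

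- The test of homogeneity finds false differences more often than its nominal level.
- The interval covers the true difference less often than stated. In a trial with an equivalence aim, it then falls inside the limits too easily.
- In the two logistic models, p-values tend to be too small for factors that do not vary within a patient.

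The stated 80% power is also at risk if the sample size has no room for the extra variance.

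**Working it through.** **Inputs from the documents.** Section 5, Sample size: rate p = 0.10 in both groups, margin 0.07, α 5%, power 80%, losses 20%. Section 5, Randomization: 1:1 allocation by patient.

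**Step 1: reproduce the plan's figures.** For equivalence of two proportions by two one-sided tests, with independent lesions and 5% for each test:

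n = 2p(1−p)(z₀.₉₅ + z₀.₉₀)² / margin² = 0.18 × (1.645 + 1.282)² / 0.0049 = 314.6 with unrounded quantiles, so 315.

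Power at 315 is 80.07%. The loss step is 315/0.8 = 393.75, so 394. Both figures are reproduced, and neither contains a design effect. The match also implies equivalence judged by a 90% interval within ±7 points, a rule that section 7 does not state.

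**Step 2: design effect (assumed inputs).** Suppose 50%, 27%, 15% and 8% of patients have 1, 2, 3 and 4 lesions.

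- E[m] = 0.50 + 0.54 + 0.45 + 0.32 = 1.81
- E[m²] = 0.50 + 1.08 + 1.35 + 1.28 = 4.21
- Design effect (DE) = 1 + (4.21/1.81 − 1) × ICC = 1 + 1.326 × ICC

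**Step 3: power with the correct variance, 90% interval rule.**

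Power = 2Φ(0.07/√(0.18 × DE/n) − 1.645) − 1.

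Example at n = 315, ICC 0.10: the standard error is √(0.18 × 1.1326/315) = 0.02544; 0.07/0.02544 − 1.645 = 1.107; power = 2 × 0.8658 − 1 = 73.2%.

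| ICC | DE | Power at 315 | Power at 350 | Power at 394 | Evaluable per group for 80% (314.6 × DE) |
|---|---|---|---|---|---|
| 0.05 | 1.066 | 76.6% | 82.1% | 87.3% | about 335 |
| 0.10 | 1.133 | 73.2% | 79.1% | 84.8% | about 356 |
| 0.20 | 1.265 | 66.2% | 72.8% | 79.5% | about 398 |
| 0.30 | 1.398 | 59.5% | 66.6% | 73.9% | about 440 |

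The largest design effect that keeps 80% power is n/314.6: 1.11 at 350 and 1.25 at 394.

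**Step 4: error rates of the planned, unclustered analysis.** The standard error is too small by 1 − 1/√DE, which is 3% at DE 1.066 and 15% at DE 1.398. A beta-binomial simulation (315 lesions per arm, 40,000 trials per setting) gave:

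| ICC | False differences, z test at 5% | Coverage of nominal 95% interval | False equivalence at 17% vs 10%, 90% interval | Same, 95% interval |
|---|---|---|---|---|
| 0 | 5.2% | 94.8% | 5.1% | 2.4% |
| 0.05 | 5.8% | 94.2% | 5.7% | 2.9% |
| 0.10 | 6.6% | 93.4% | 6.5% | 3.3% |
| 0.20 | 8.2% | 91.7% | 7.2% | 4.0% |
| 0.30 | 9.9% | 90.1% | 8.4% | 4.9% |

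With a cluster-robust standard error, the false-difference rate stayed at 5.0% to 5.2%.

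**Step 5: other assumptions.** Using DE = 1 + (m − 1) × ICC, with m = 1.2 to 2 lesions per patient and ICC 0.1 to 0.3, DE runs from 1.02 to 1.30 and power at 315 from 79.0% to 64.4%. At DE 1.025 (for example m = 1.5, ICC 0.05), power at 315 is 79% and the standard error is 1.2% too small.

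**The case against.** **The loss allowance may hide spare lesions.** The 20% includes failed cold polypectomies, yet section 7 discards these from neither analysis: intention to treat keeps them in their arm, and the per-protocol analysis moves them to the hot group. They are also no loss mechanism for the hot arm. If only unrecovered specimens are lost, and these are 5% rather than 20% (an assumption), 394 × 0.95 = 374 per group remain. Power is then 85% at DE 1.066 and 82% at DE 1.133. This stands as a reason not to read the 315 column alone. But the slack is accidental, the per-protocol cold group still shrinks, and extra lesions do not repair an understated standard error.

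**The size rests on invented inputs.** This also stands. Nothing in the documents supports half of patients having two or more eligible lesions, or an ICC of 0.30. The 60% power and 9.9% error are the extreme corner of the illustration.

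**The decision rule is not stated.** Under a 95% interval rule, false equivalence stays at 4.9% or below across the range, within the stated 5%. Power at 315 is then about 67% with no clustering at all, so the missing rule can cost more than mild clustering. That is a separate defect and does not remove this one.

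**Endoscopist is a stratum and a candidate confounder.** Adjustment might absorb some of the correlation. However, the primary z test is unadjusted, and screening for changes in the odds ratio does not correct a standard error for correlation within patients.

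**Conclusion.** The concern holds. That the plan omits clustering is certain: 315 and 394 are fully explained by independent lesions and losses, and no planned analysis accounts for patients who contribute several lesions. The direction is also certain for any positive ICC where some patients have more than one lesion: the interval is too narrow, and power at 315 is below 80%.

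The size is not known. It ranges from about one point of power and a 1.2% understated standard error at DE 1.025, to about 20 points of power and a 15% understated standard error at DE 1.40. The power figures assume a 90% interval rule. If more than 315 lesions per group are evaluable, power may still reach 80%, but the test and interval remain wrong. This should be fixed, although it need not be fatal to the trial.

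**What to change.** **Section 7, primary analysis.** Estimate the risk difference (cold minus hot) and its confidence interval with variance clustered on patient ID, and base the primary test on that standard error. A binomial GEE with identity link and robust standard errors would do, as would a risk-difference model with cluster-robust standard errors; both run in Stata 13. Clustering also covers the per-protocol analysis, where reassigned lesions can place one patient in both groups.

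**Section 7, secondary models.** Cluster the logistic models for incomplete excision and failed cold polypectomy on patient ID in the same way.

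**Section 5, Sample size.** State that 315 and 80% hold only for independent lesions. Give the assumed lesions per patient and ICC, and replace the single power figure with a table over design effects (for example 1.0 to 1.4) and evaluable lesions (315, 350, 394).

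**Cost.** Wording and a small table; section 6 already assigns a patient ID. The price is a wider interval and a less favourable stated power. Rewording adds no lesions: if the sponsor's assumed design effect puts power below 80%, it must accept that or raise the target, for example to the evaluable numbers in the last column of the power table.
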